### **2.3.2 Exploratory Efficacy Endpoints**

The following exploratory efficacy endpoints will be assessed at 6 and 12 months post infusion or reference date:

- 1) Change from baseline in cardiac structural parameters measured by magnetic resonance imaging (MRI), including:
  - LV late gadolinium enhancement (LGE) expressed as a percent of LV mass
  - LV LGE expressed in grams
  - LV viable mass expressed in grams
  - Number of LV segments with LGE
  - LV circumferential strain
  - Left ventricular ejection fraction (LVEF)
  - LV end diastolic volume (LVEDV) and LV end systolic volume (LVESV)
  - LV stroke volume
  - Regional LV function assessment

LGE and circumferential strain will be assessed both overall as well as by individual segment and by groups of segments (e.g., infusion location, septum, base, LV free wall).

- 2) Rate of change since baseline compared to rate of change from historical MRI to baseline in LV LGE (overall and by individual segment and groups of segments)
  - expressed as a percent of LV mass
  - expressed in grams
- 3) Change from baseline in functional parameters:
  - Performance of Upper Limb (PUL) scale
  - Spirometry
  - 6-minute walk test (6MWT) in ambulatory patients
- 4) Change from baseline quality of life (QoL) parameters:
  - Pediatric Quality of Life Inventory (PedsQL), including the cardiac module
  - Pediatric Outcomes Data Collection Instrument (PODCI) Adolescent Questionnaire
- 5) Change from baseline in biomarkers:
  - Osteopontin
  - ST2
  - Interleukin 10 (IL-10)
  - Galectin-3

[figure not shown]

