# 10. EXPLORATORY EFFICACY ANALYSIS

Listings of efficacy parameters will be done for the ITT population. Summaries and analyses will primarily be done for the mITT population; some or all summaries and/or analyses may also be done for other analysis populations defined in [Section 6](#). In addition, “last observation” analyses will be done for certain parameters for which some subjects’ final assessments were done too late to be included in the Month 12 analysis window.

Unless otherwise noted, for the final analysis changes from baseline will be analyzed using general linear models with baseline values as covariates. Analyses of the effect of treatment group, time (baseline, Month 6, Month 12), and their interaction will be done using mixed effects linear regression, with subject as a random effect, time and treatment group as fixed effects, and baseline as a covariate. Study site may also be included as a random effect if there is evidence of correlation within study sites (per the interclass correlation coefficient from the unconditional model) and/or if doing so appreciably improves the model fit (e.g., per Akaike’s Information Criterion). Residuals will be evaluated for substantial departure from normality and independent and constant variance and appropriate remedies (e.g., data transformations, detecting and assessing the influence of outliers, alternative analytical approaches) will be attempted when necessary. An unstructured covariance will be the default covariance structure but other structures (e.g., compound symmetry) may be used to evaluate sensitivity to the choice of structure or, if necessary, to achieve convergence.

For the analysis of LV LGE rate of change since baseline compared to rate of change from historical MRI to baseline, rate of change  $RC(t_i)$  for time point  $t_i$ ,  $i = 1$  to 3 (baseline, Month 6, Month 12, respectively), will be calculated as

$$RC(t_i) = (X(t_i) - R(t_i)) / D(t_i)$$

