where  $X(t_i)$  is observed LGE at  $t_i$ ,  $R(t_i)$  is observed LGE at the reference time point for  $t_i$ , and  $D(t_i)$  is the number of days between  $t_i$  and the reference time point for  $t_i$ . The reference time point will be the date of historical MRI for  $i = 1$  and baseline for  $i > 1$ . The mixed effects model to be used for the final analysis will be similar to that described above, with historical LGE included as a covariate. The LSMEANS procedure in PROC MIXED will be used to compare  $RC(t_2)$  and  $RC(t_3)$  to  $RC(t_1)$  within each treatment group, and tests for interaction along with descriptive statistics will be used to evaluate differences by treatment group.

Assuming missing observations are “missing at random” (MAR), i.e., the fact that they are missing is unrelated to the missing variable but can be related to another variable on which data have been collected, the maximum likelihood (ML) approach is able to handle subjects with either Month 6 or Month 12 changes from baseline missing, but not both. Therefore, for final analyses based on the mITT population, missing data will be addressed using ML. Final analyses based on the ITT population may include subjects with both Month 6 and Month 12 changes from baseline missing; under these circumstances, multiple imputation will be used based on all observations and will use a fully conditional specification method with 20 burn-in iterations and the regression method of imputation. Variables in the imputer’s model will be baseline observation (because baseline is used as a covariate in analyses), Month 6 change from baseline, Month 12 change from baseline, and treatment group. Because the MAR assumption is not testable, and because it seems possible that subjects with poorer outcome may be more likely to miss trial assessments, a sensitivity analysis under a “missing not at random” (MNAR) assumption may be done (for the final analysis only) for any efficacy endpoint for which all change from baseline measurements are missing for some subjects. For the MNAR model, multiple imputation will use the pattern-mixture model approach to address missing values; i.e., the imputation will be based on a pre-specified subset of subjects: for this MNAR analysis, only subjects randomized to usual care. Because very few missing observations are expected in this trial, 5 imputed data sets will be used for all analyses using multiple imputation.

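### The planned between-arm test of the LGE rate endpoint treats the pre-randomization rate as an outcome, which can cost much of its power; using that rate as a covariate avoids the loss.

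*SAP*

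**What the plan says.** SAP 2.3.2 lists as an exploratory endpoint "Rate of change since baseline compared to rate of change from historical MRI to baseline in LV LGE", as a percent of LV mass and in grams.

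SAP 10 defines RC(t_i), for i = 1 to 3, as the LGE difference from a reference scan divided by the days between the two scans. "The reference time point will be the date of historical MRI for" the first index; at Months 6 and 12 the baseline scan takes that place. RC(t1) is therefore fixed before Day 0. The rate model is "similar to that described above, with historical LGE included as a covariate". The model referred to has three time levels: "Analyses of the effect of treatment group, time (baseline, Month 6, Month 12), and their interaction will be done using mixed effects linear regression". Its terms are a random subject effect, fixed effects of visit and arm, and an adjustment for the baseline value. On covariance, "An unstructured covariance will be the default covariance structure".

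For this endpoint, LSMEANS is assigned to the comparison of the two post-baseline rates with RC(t1) inside each arm. For the comparison of the arms, "tests for interaction along with descriptive statistics will be used to evaluate differences by treatment group".

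Four other provisions matter:
- SAP 10 ends with a general rule that tests of treatment effect for all efficacy parameters rest on LS-mean comparisons.
- SAP 10.1 gives between-arm p-values for changes from baseline in the MRI parameters, LGE included.
- Protocol 6.8.4 makes the historical scan optional. It asks for the most recent scan taken at least 6 weeks before screening and sets no maximum age.
- SAP 4 gives about 12 subjects per arm, with no SD, effect size or power.

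**The concern.** The between-arm question is whether the post-baseline rate differs by arm. The interaction instead estimates the arm difference in RC(t2) or RC(t3) minus the arm difference in RC(t1). Randomization makes the second term zero in expectation, so subtracting it leaves the target unchanged and brings in the sampling error of RC(t1).

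The structure of the rates aggravates this. The baseline scan enters RC(t1) with a plus sign and RC(t2) and RC(t3) with a minus sign. Its error therefore pushes the pre- and post-baseline rates in opposite directions, and their difference becomes noisier.

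The historical-LGE covariate does not repair it. It is a level, not a rate, and with one slope common to all time levels it cancels out of the within-subject contrast when data are complete. At stake is the precision of the one LGE analysis that uses the historical scans.

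**Working it through.** **Inputs.** From the documents: about 12 per arm (SAP 4), two-sided 0.05 (SAP 7.3), follow-up MRI at Months 6 and 12, and a minimum history of 6 weeks (Protocol 6.8.4). Assumed, because not stated: every subject has all scans; scan errors are independent with SD 1; subject slopes are stable with SD τ per year, τ = 0, 1, 2, 4; the history is d years. Six weeks is taken as 1.5 months (d = 0.125). The plan has no power figure to reproduce.

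**Variances at Month 12** (follow-up f = 1 year):
- Var RC(t1) = τ² + 2/d²
- Var RC(t3) = τ² + 2/f²
- Cov = τ² − 1/(d·f), the negative term coming from the shared baseline scan
- Interaction contrast: V_int = Var RC(t1) + Var RC(t3) − 2·Cov = 2/d² + 2/f² + 2/(d·f)
- ANCOVA on RC(t1): V_anc = Var RC(t3) − Cov²/Var RC(t1)

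**Example, d = 1, τ = 0.** Var RC(t1) = Var RC(t3) = 2 and Cov = −1, so the correlation is −0.5. V_int = 2 + 2 + 2 = 6. V_anc = 2 − 1/2 = 1.5. The variance ratio is 4, so the SE ratio is 2.0.

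**Power.** With 12 per arm, ANCOVA (21 df) reaches 80% at a non-centrality of 2.938. Its variance carries a factor 1 + 1/20 = 1.05 for estimating the covariate coefficient. At the same effect the interaction contrast (22 df) has non-centrality 2.938 × √(1.05 × V_anc/V_int). For the example this is 2.938 × √(1.05/4) = 1.505, which gives 30% power.

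Power of the Month 12 interaction contrast where ANCOVA has 80% (V_int/V_anc in parentheses):

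| History | τ = 0 | τ = 1 | τ = 2 | τ = 4 |
|---|---|---|---|---|
| 6 weeks | 6% (97) | 7% (56) | 9% (25) | 17% (8.3) |
| 3 months | 8% (28) | 11% (15) | 19% (7.0) | 41% (2.8) |
| 6 months | 16% (9.3) | 26% (4.8) | 45% (2.5) | 67% (1.4) |
| 12 months | 30% (4.0) | 53% (2.0) | 70% (1.3) | 79% (1.1) |
| 15 months | 36% (3.2) | 61% (1.6) | 75% (1.2) | 80% (1.05) |

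A joint 2-df interaction test is weaker still. At 12 months it has 22, 40, 57 and 66%, computed without the 1.05 factor, which moves the contrast figures by about two points at most.

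**Checks.** In simulation (4,000 trials per case) null rejection was 4.3–5.9%, so the size holds. A separate simulation (1,500 runs) fitted the unstructured model with historical LGE as a covariate, at d = 12 months and τ = 0. The interaction contrast had 30% power, the 2-df test 23%, ANCOVA on RC(t1) 78%, and the direct LS-mean arm difference at Month 12 in the same model 69%.

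**Direction.** The interaction is an adjustment for RC(t1) with the coefficient fixed at 1; ANCOVA estimates it. In large samples ANCOVA therefore cannot have the larger variance, whatever the error correlations. Only the size of the gain depends on the assumptions above.

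**The case against.** The strongest reply is that the plan already tests what matters. SAP 10.1 compares LGE change from baseline between arms, and RC(t2) and RC(t3) are those changes divided by nominally 180 and 360 days. That test never subtracts RC(t1). The general LS-mean rule in SAP 10 may also allow a direct arm comparison at Months 6 and 12 inside the rate model.

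This largely stands. A reader might infer that a real slowing of scar growth would usually be missed, but the documents do not support that. With scan noise alone, an unadjusted comparison of post-baseline rates has about 70% power where ANCOVA has 80%. Over 40 assumed cases, at least one of the interaction and the unadjusted comparison had 67% or more. The change-from-baseline tests do leave the historical rate unused. Whether the LS-mean rule reaches the rate endpoint is unclear, since the endpoint's own text gives the between-arm question to the interaction.

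Other replies:
- *The interaction is the endpoint as defined.* The pre/post comparison can stay as description. Under randomization both methods target the same expected treatment effect.
- *Independent scan error is doubtful.* This is fair: SAP 10.1 has readers use earlier images, and the documents do not say how historical scans are read. The table's figures would change; the direction would not.
- *The covariate loses subjects without a history.* The planned rate model already needs historical LGE, so nothing further is lost. But if only 8 of 12 per arm have a history, with scan noise alone and equal intervals, the ANCOVA variance is 2(1.5)/8 = 0.375 against 2(2)/12 = 0.333 for the unadjusted all-subject comparison. That is a reason to keep the all-subject test.
- *The history will vary between subjects.* True; the calculation varies it only between scenarios.

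**Conclusion.** The concern holds as a conditional loss of efficiency in one exploratory test. A variable fixed before randomization is used as a response level, and the named between-arm test subtracts it. Size is preserved.

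A reader might conclude that most of the power is always lost. The documents give no scan error, slope variability or distribution of historical intervals, so that cannot be said. Under the assumptions shown, the loss is severe at 6 weeks for every τ tried, ranges from severe to modest at 6 months, and nearly vanishes at 12 months or more when stable slopes dominate. In that last setting (12 months, τ = 4) the interaction beats an unadjusted comparison by a wide margin, 79% against 36%.

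ANCOVA on RC(t1) matched or beat the interaction in every case, to within about a point. It falls about two points below the unadjusted comparison when the two rates are nearly uncorrelated, because it spends a degree of freedom. Safety is the primary objective and no efficacy power is claimed, so severity is low.

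**What to change.** In SAP 10, among subjects with a historical scan, make the between-arm test of this endpoint a mixed model with RC(t2) and RC(t3) as the only responses. Include treatment, visit, treatment-by-visit, and RC(t1) as a covariate with a separate coefficient at each visit. Report LS-mean arm differences at Months 6 and 12.

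Keep the within-arm pre/post comparison and the three-level interaction as descriptive. Keep the all-subject LGE change-from-baseline test of SAP 10.1 alongside.

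State also whether baseline LGE stays in the rate model next to historical LGE: given the interval, the two together determine RC(t1) exactly. Report how many subjects per arm have a historical scan and how the intervals are distributed.

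The cost is a change of SAP wording and one PROC MIXED call. No new data are needed, and no subjects are lost relative to the planned rate model.

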### 3. STUDY DESIGN AND SCHEDULE OF EVENTS

This is a randomized, open-label, controlled phase 2 trial designed to evaluate the safety and tolerability and explore the efficacy of CAP-1002 administered by multi-vessel intracoronary infusion in subjects with cardiomyopathy secondary to DMD. Approximately 24, and not more than 30, subjects will be randomized 1:1 to receive CAP-1002 or usual care. Subjects randomized to receive usual care will continue to be cared for and treated on an ongoing basis in whatever manner the investigator deems most appropriate for the subject. The first 6 subjects enrolled (Group 1) will be older than 18 years of age. Enrollment of the remaining subjects (Group 2) will begin at least two weeks after the final infusion occurs in Group 1 to allow a review of Group 1 safety data through 72 hours post infusion. Subjects in Group 2 will be at least 12 years of age.

CCI

Anatomically  
one of the three coronary arteries infused must supply more than 30% of the LV myocardium.

Subjects will undergo protocol assessments through 12 months post infusion or reference date. Reviews by a Data Safety Monitoring Board (DSMB) will be done after Group 1 completes 72 hours of follow-up and throughout the trial per charter but at least semi-annually. The DSMB will review both safety and efficacy data after all subjects complete 6 months of follow-up or withdraw from the study. In addition, there will be one administrative interim efficacy analysis after Month 6 MRI measurements are available for at least 14 subjects. Subjects will be followed annually for 5 years post infusion or reference date. The Schedule of Events is shown in [Appendix A](#). A schematic of the study design is as follows:

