## 4. SAMPLE SIZE

The sample size of approximately 12 subjects per treatment group is adequate to assess safety and tolerability and to explore efficacy.

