### 7.3 Data Analysis

- The anchor date used for summaries and analyses will depend on the analysis population, as follows:
  - ITT population: randomization date
  - mITT population: IP administration or reference date

- Safety population: IP administration or reference date
- Per protocol population: IP administration or reference date
- Categorical variables will be summarized as frequencies and percentages in each category. Percentages will be reported to one decimal place. Unless otherwise noted in Sections 8-10, categorical variables will be analyzed using chi square tests of association or, if any contingency table cell has less than 5 subjects, Fisher's exact test.
- Continuous variables will be summarized by numbers of subjects, means, standard deviations, medians, and ranges. The number of decimal places for minimums and maximums will be the same as the original data. The number of decimal places for means, medians, and interquartile ranges will be the same as the original data plus one. The number of decimal places for measures of variance will be the same as the original data plus two. Unless otherwise noted in Sections 8-10, continuous variables will be analyzed using t-tests or, if appropriate, analysis of covariance with baseline as a covariate. Non-parametric tests and data transformations will be considered for variables with distributions that violate parametric assumptions.
- Data with qualifiers (e.g., “<”) will be listed with but summarized without the qualifier.
- P-values will be presented to two decimal places if  $> 0.01$ , to three places if  $< 0.01$  but  $> 0.001$ , and to four places if  $< 0.001$  but  $> 0.0001$ . P-values  $< 0.0001$  will be presented as “ $< 0.0001$ .”
- Statistical tests will be two-sided and tested at the 0.05 significance level unless otherwise noted in Sections 8-10.
- It is understood that statistical non-significance is not an indicator of equivalence.

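### SAP 10 names maximum likelihood for the final mITT analyses and gives no degrees-of-freedom method; if the mixed models are fitted that way with about 24 subjects, 0.05 tests run at roughly 6 to 9%

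*SAP*

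**What the plan says.** SAP 10 plans two kinds of efficacy analysis.

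- Under the first, "for the final analysis changes from baseline will be analyzed using general linear models with baseline values as covariates".
- The second is a mixed effects linear regression for treatment, time and their interaction, "with subject as a random effect, time and treatment group as fixed effects, and baseline as a covariate". On its covariance: "An unstructured covariance will be the default covariance structure".

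On missing data, SAP 10 says that under a missing-at-random (MAR) assumption "the maximum likelihood (ML) approach is able to handle subjects with either Month 6 or Month 12 changes from baseline missing, but not both". It concludes: "Therefore, for final analyses based on the mITT population, missing data will be addressed using ML". The SAP's abbreviation list expands ML as maximum likelihood. ITT analyses with both visits missing, and the sensitivity analysis under missing-not-at-random, use multiple imputation instead.

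PROC MIXED with LSMEANS is named for the LGE rate-of-change model, without an estimation or degrees-of-freedom option. Treatment tests are LS-mean comparisons without multiplicity adjustment. SAP 7.3 sets the level: "Statistical tests will be two-sided and tested at the 0.05 significance level unless otherwise noted in Sections 8-10". SAP 3 gives the size: "Approximately 24, and not more than 30, subjects will be randomized 1:1 to receive CAP-1002 or usual care".

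**The concern.** Full maximum likelihood estimates residual variance without allowing for the mean parameters that have been fitted. In a large trial this is negligible. With about 12 subjects per arm it makes standard errors visibly too small, and the stated 0.05 level is then not the level at which the tests run. A normal reference in place of a t reference would add to the excess, and the SAP does not say which applies.

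The reason the SAP gives for ML is validity under MAR when one of the two visits is missing. REML has the same property, so ML gains nothing here. At stake are the p-values and intervals from the mixed models, which the SAP's Preface allows to be carried into manuscripts.

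**Working it through.** **Inputs.** n is about 24 and at most 30 (SAP 3). The level is 0.05, two-sided (SAP 7.3). With intercept, treatment and baseline at a visit, the mean parameters number p=3. The SAP expects very few missing observations but gives no rate, so 0% and 8% per visit are assumed. It gives no SD, effect size, power or standard error. The only stated figure is therefore the 0.05 level, which a general linear model with a t test on n-p degrees of freedom meets by construction.

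**Step 1: closed form.** The ML standard error divided by the unbiased one is r = sqrt((n-p)/n). The actual level is P(|t with n-p df| > c × r), where c is the critical value used: the t quantile on n-p df, or 1.96.

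For n=24, p=3: r = sqrt(21/24) = 0.935, so the standard error is 6.5% too small.

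| n | p | SE ratio | Level, t reference | Level, normal reference |
|---|---|---|---|---|
| 30 | 3 | 0.949 | 6.2% | 7.4% |
| 24 | 3 | 0.935 | 6.5% | 8.1% |
| 20 | 3 | 0.922 | 6.9% | 8.9% |

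**Step 2: the longitudinal model.** The closed form is a per-visit calculation, so the mixed model was simulated under the null. The model had two post-baseline visits, unstructured covariance with correlation about 0.5, treatment, time, interaction and baseline. There were 3000 runs at n=24, with Monte Carlo error of about 0.4 to 0.5 points. The SE ratio is model-based over empirical, and t is on n-3 df.

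| n=24, contrast | Missing per visit | ML SE ratio | ML, t | ML, normal | REML, t | REML, normal |
|---|---|---|---|---|---|---|
| Month 12 | 0% | 0.943 | 6.1% | 7.5% | 4.8% | 6.0% |
| Month 12 | 8% | 0.917 | 6.9% | 8.6% | 5.3% | 6.9% |
| Visit average | 0% | 0.924 | 6.6% | 8.7% | 5.3% | 6.5% |
| Visit average | 8% | 0.900 | 7.0% | 9.0% | 5.1% | 6.8% |
| Interaction | 0% | 0.979 | 5.3% | 6.6% | 4.3% | 5.6% |
| Interaction | 8% | 0.923 | 7.0% | 8.6% | 5.9% | 7.1% |

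With a more generous t reference on 2n-5 df, the ML figures for n=24 lie between 5.9% and 7.9%. At n=20 with 8% missing (2000 runs), ML gives 7.2 to 8.0% on n-3 df and up to 9.9% with a normal reference; REML on n-3 df gives 5.6 to 6.1%.

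The last column shows that REML alone is not enough: with a normal reference it still runs at 5.6 to 7.1%. The estimator and the degrees of freedom both need stating.

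**Step 3: smaller subsets.** The 6MWT uses ambulatory subjects only (SAP 10.2.3). The rate-of-change model needs a historical MRI, which is collected only where available (Protocol 6.8.4), and adds historical LGE as a covariate. Subset sizes are not given. Taking n=14 as an assumption:

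- p=3: r = sqrt(11/14) = 0.886; level 7.7% (t) to 11.0% (normal).
- p=4, as an approximation to the rate-of-change model: r = sqrt(10/14) = 0.845; level 8.9% to 12.9%. The same p at n=20 gives 7.6% to 9.9%, and at n=24 gives 7.1% to 8.9%.

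**The case against.** **The sentence is about missing data, not about the estimator.** Its paragraph contrasts likelihood handling with multiple imputation. It does not weigh ML against REML, and the paragraph that specifies the mixed model names no estimator. This stands: a reader might infer that the SAP deliberately chose ML over REML and rejected a small-sample correction, and the text supports neither. The second is silence. But the abbreviation is defined as maximum likelihood, no separate ML step is described, and a literal programmer would fit by ML. If the word is loose, two programmers could report different p-values from the same plan. The software's default setting is not in the documents and is not relied on here.

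**Much of the efficacy output is not exposed.** A reader might infer that every efficacy p-value is anti-conservative. SAP 10 does not support that. Its first rule is a general linear model of change from baseline, and the p-values tabled for MRI, PUL, spirometry, 6MWT and QoL are described as comparisons of change from baseline, which fits that rule. Ordinary t tests there hold 5%. LS-mean comparisons suit either model. This stands and limits the point to the mixed models.

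**The headline ratio comes from a per-visit form.** True of Step 1, but the two-visit simulation gives much the same result for the Month 12 and visit-averaged contrasts.

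**The upper figures need a normal reference that the SAP does not state.** This stands: 8 to 9% at n=24 is the outer case.

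**Efficacy is exploratory.** SAP 4 says only: "The sample size of approximately 12 subjects per treatment group is adequate to assess safety and tolerability and to explore efficacy". No efficacy hypothesis is designated primary, and the unadjusted multiplicity over many parameters is a larger source of chance findings than an excess of one or two points per test. This stands, and it sets the weight of the point.

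**Conclusion.** The point holds conditionally. If the mixed models are fitted by full maximum likelihood, as the wording of SAP 10 most plainly reads, and nothing is done about degrees of freedom, then at n=24:

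- standard errors are about 6% too small with complete data, and about 8% too small for the Month 12 contrast with 8% missing;
- tests at the stated 0.05 run at roughly 6 to 7.5% with a t reference (7.9% at most among those tried) and up to about 8 to 9% with a normal reference;
- the interaction test with complete data is barely affected at 5.3%, while smaller subsets do worse.

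This covers the mixed-model LS-mean and interaction tests, including the LGE rate-of-change model, and nothing else. The figures assume normal errors, two post-baseline visits and the missing-data rates above; the n=14 figures rest on an assumed subset size. The effect is modest in an exploratory analysis, but the remedy is cheap and also removes an ambiguity in the prespecification.

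**What to change.** In SAP 10, replace the sentence "Therefore, for final analyses based on the mITT population, missing data will be addressed using ML" with:

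*Incomplete data in the final mITT analyses will be handled by likelihood-based estimation under MAR. The mixed models will be fitted by REML with Kenward-Roger degrees of freedom; ML will be used only to compare models with different fixed effects.*

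The planned check on whether to add study site as a random effect leaves the fixed effects unchanged, so it can be done under REML.

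The cost is one sentence and two PROC MIXED options. Intervals widen by about 6 to 8% with the same t reference: 0.999/0.943 = 1.06 for Month 12 at n=24 with complete data, and 0.972/0.902 = 1.08 at n=20 with 8% missing. In the simulation, REML with a t reference on n-3 df brought n=24 tests to 4.3 to 5.9%. That reference stood in for Kenward-Roger, which was not itself simulated.

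### With only 5 imputed data sets, borderline p-values from the optional ITT and MNAR efficacy analyses can change side of 0.05 with the random seed

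*SAP*

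**What the plan says.** SAP Section 10 divides missing efficacy data between two methods.

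- **Main analysis.** "Summaries and analyses will primarily be done for the mITT population", and "for final analyses based on the mITT population, missing data will be addressed using ML". Maximum likelihood (ML) uses subjects who have at least one of the two follow-up changes.
- **ITT analysis.** "Final analyses based on the ITT population may include subjects with both Month 6 and Month 12 changes from baseline missing". In that case the SAP uses multiple imputation by fully conditional specification, with baseline, the two changes and treatment group in the imputation model. ITT analyses are optional under Section 10.
- **MNAR sensitivity analysis.** Also optional, at the final analysis only, and limited to endpoints for which some subjects have no change from baseline at all. Values are imputed from usual care subjects alone.

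The number of imputations is the same throughout: "Because very few missing observations are expected in this trial", "5 imputed data sets will be used for all analyses using multiple imputation". Neither document states a missing-data rate, a random seed or a tolerance for Monte Carlo error. On testing, Section 7.3 says: "Statistical tests will be two-sided and tested at the 0.05 significance level unless otherwise noted in Sections 8-10".

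**The concern.** Having few missing values is a good reason to expect 5 imputations to estimate the treatment effect efficiently. It does not follow that the p-value will be stable. Multiple imputation is used here for subjects with neither follow-up value, and in a trial this small ("Approximately 24, and not more than 30, subjects will be randomized 1:1 to receive CAP-1002 or usual care") even one such subject carries visible weight. With 5 random draws, both the pooled estimate and the between-imputation variance depend on the seed.

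If the ITT or MNAR analysis gives a borderline p-value, its side of 0.05 may reflect the seed and not the data. A reader could not tell from the report which it was. The MNAR analysis is also the plan's own check on the missing-at-random assumption, which the SAP calls untestable.

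**Working it through.** The plan has no figure to reproduce: 5 is a choice, and neither document gives a power or Monte Carlo calculation.

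**Inputs from the documents.** m = 5 imputations (SAP Section 10); two-sided 0.05 (SAP Section 7.3); about 24 subjects (SAP Section 3), hence about 24 − 2 = 22 degrees of freedom.

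**Assumed inputs.** 1 to 3 subjects lack both follow-up values, with a fraction of missing information (FMI) of 5% to 14%. The FMI range comes from the simulation described below.

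**Efficiency.** Relative efficiency is 1/(1 + FMI/m). With m = 5 this is 1/(1 + 0.05/5) = 0.99 and 1/(1 + 0.14/5) = 0.97. On this measure the SAP's reason holds.

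**Stability, simple formula.** Let B be the between-imputation variance and T the total variance. Then FMI ≈ (1 + 1/m)B/T, and the Monte Carlo variance of the pooled estimate is B/m. In standard-error units, the Monte Carlo SD is therefore √(FMI/(m + 1)).

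Take a p-value that would be 0.04 with very many imputations. With 22 degrees of freedom this is t = 2.183; the 0.05 boundary is t = 2.074. The 95% Monte Carlo range is the p-value at 2.183 ± 1.96 × SD.

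| FMI | m | Monte Carlo SD | t range | p range |
|---|---|---|---|---|
| 5% | 5 | √(0.05/6) = 0.091 | 2.004 to 2.362 | 0.027 to 0.058 |
| 14% | 5 | √(0.14/6) = 0.153 | 1.883 to 2.482 | 0.021 to 0.073 |
| 5% | 50 | √(0.05/51) = 0.031 | 2.122 to 2.244 | 0.035 to 0.045 |
| 14% | 50 | √(0.14/51) = 0.052 | 2.080 to 2.286 | 0.032 to 0.049 |

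With m = 5 both ranges include 0.05; with m = 50 neither does. Starting from p = 0.01 (t = 2.819), the worst of these cases reaches t = 2.819 − 1.96 × 0.153 = 2.519, where p is still below 0.02.

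**Stability, simulation.** The formula leaves out noise in the between-imputation variance and the degrees of freedom, so it understates the spread. The SAP's procedure was therefore simulated with 24 to 30 subjects, 1 to 3 of them lacking both visits, and an assumed Month 6 to Month 12 correlation of 0.6. The analysis was a Month 12 ANCOVA pooled by Rubin's rules with Barnard-Rubin degrees of freedom. FMI came out at about 0.05 to 0.14. The table shows the share of seeds with m = 5 that land on the other side of 0.05 from the 2,000-imputation result.

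| p with 2,000 imputations | Missing at random (MAR) | MNAR |
|---|---|---|
| about 0.01 | 0–1% | 0–3% |
| about 0.03 | 7–20% | 12–23% |
| about 0.04 | 22–37% | 27–41% |
| about 0.06 | 20–32% | 27–37% |
| about 0.08 | 1–10% | 5–15% |

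With a single subject missing out of 24 under MAR and p about 0.04, the 5th to 95th percentile range was 0.028 to 0.067.

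Near p = 0.04, the SD of the p-value falls from 0.013–0.029 with m = 5 to about 0.004–0.007 with m = 50 and 0.002–0.005 with m = 100. With m = 100, crossing there falls to 0–5% under MAR and 1–5% under MNAR, apart from one MNAR case that sat at p = 0.045 (15%).

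**The case against.** The case for leaving the text alone has several parts, and most of them stand as limits on the point.

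- **Missing data are also handled elsewhere.** A reader might infer that the ITT and MNAR analyses are the only ones that deal with missingness. They are not: the main mITT analysis uses ML, which covers a subject with one missing visit and has no Monte Carlo noise.
- **Imputation may never be used.** Both affected analyses are optional. If no subject lacks both values, the SAP's stated trigger for imputation is not met.
- **Not being infused does not mean having no data.** A reader might count every randomized but uninfused subject as needing imputation. The protocol follows all randomized subjects for a year (synopsis, Duration of Follow-Up), and SAP Section 7.6 sets Day 0 by planned infusion, so those who stay on study have observed values. Some who withdraw also supply one: protocol Section 7.11 asks for the Month 12 assessments, with an MRI if the last was at least 12 weeks earlier, and the SAP's Month 6 analysis window is Days 154 to 275.
- **No confirmatory decision depends on it.** Efficacy is exploratory, and Section 4 says only: "The sample size of approximately 12 subjects per treatment group is adequate to assess safety and tolerability and to explore efficacy".
- **No number of imputations settles a result at exactly 0.05.** Such a result falls on either side about half the time whatever m is. A larger m narrows the zone of doubt without removing it.

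These arguments lower the severity. They do not supply a reason for 5: the SAP's stated reason concerns efficiency, and the instability appears even with one subject imputed.

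**Conclusion.** The point holds as a conditional one of low severity. If the ITT or MNAR analysis is run with 1 to 3 subjects lacking both follow-up values, 5 imputations leave borderline p-values, roughly 0.03 to 0.08, dependent on the seed. At a p-value of about 0.04, between about a fifth and two fifths of seeds would print 0.05 or more.

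The stronger reading, that ITT and MNAR results in general cannot be reproduced at the 0.05 level, is not supported. P-values near 0.01 rarely cross when few subjects are missing, and the estimates themselves lose little efficiency.

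The sizes rest on assumptions that the documents neither give nor contradict: the number of subjects lacking both visits, the resulting FMI of 5% to 14%, and the correlation between visits. More missing data would make it worse: in a stress case with 6 of 30 missing, 42–45% of seeds crossed at p about 0.04 and 5–8% at about 0.01. A different degrees-of-freedom rule in the pooling software could shift the percentages slightly.

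**What to change.** In SAP Section 10, replace 5 with at least 50 imputed data sets, for example 100, for all multiple imputation analyses, and drop the justification based on few missing values. State the random seed in the SAP. The seed makes the run repeatable but does not reduce Monte Carlo error, so the larger number is the change that matters. Reporting the Monte Carlo error of each imputed p-value would be a useful addition.

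The cost is one edited sentence and seconds of computing. Design, data collection, estimand and the main analysis are unchanged. This is a free improvement.
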